9.4 Analysis of Baseline Demographics and Procedural Characteristics

Descriptive statistics will be generated for pre-intervention demographics, aneurysm characteristics and procedural characteristics, device usage and adverse events. Categorical variables will be analyzed using frequency, incidence, and event rate. For continuous variables collected in the study, analysis will include mean, median, standard deviation, and range.

The following data points will be analyzed in this study:

- Antiplatelet therapy regimen
- Adverse events related to antiplatelet therapy
- Platelet reactivity testing results
- Moderate and Severe bleeding events utilizing GUSTO criteria
- All intracranial hemorrhages and delayed intracranial hemorrhages (>30 days post-procedure)
- Index procedure time
- Number of Pipeline™ Flex Embolization Device with Shield Technology™ utilized
- Device deployment success rate at target site
- Aneurysm occlusion at 6 months, 1 year and at last follow-up
- Recurrence and retreatment rates at 1 year post-procedure and at last follow-up

- The composite percentage of patients with modified Rankin Scale of 0-2 or no change from baseline at 1 year and at last follow-up.
- Occurrence of major stroke in the territory supplied by the treated artery or neurological death.

Major Stroke events will be further characterized based on whether:

- Event was caused by thromboembolic events
- Event was caused by side-branch occlusion due to the study device

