Intra-Cranial Hemorrhage (ICH)	
Intra-Cranial hemorrhage is defined as hemorrhage within the fixed vault of the cranium (skull).
 
Intra-Cranial Hemorrhage will be further categorized by the CEC as:
 
 o Intra Cerebral Hemorrhage (further categorized as): 
 ▪ Intra-Parenchymal Hemorrhage (IPH): Bleeding within the cerebral matter (brain parenchyma), not involving the ventricles. ▪ Intra Ventricular Hemorrhage (IVH): hemorrhage within the ventricles o Sub Arachnoid Hemorrhage (SAH): Bleeding into the subarachnoid

TERM	DEFINITION
	
space—the area between the arachnoid membrane and the pia mater surrounding the brain
 
 ○ Subdural Hematoma (SDH): Occurs when there is tearing of the bridging vein between the cerebral cortex and a draining venous sinus ○ Epidural Hematoma (EDH): A rapidly accumulating hematoma between the dura mater and the cranium

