Subjects will be considered enrolled in the study once the patient has signed and dated the Informed Consent or DRF and the Pipeline™ Flex Embolization Device with Shield Technology™ is advanced into the micro catheter inside the patient. All enrolled subjects who underwent the study procedure and in whom an attempt to implant the device was made will be included in the analysis population.

A CEC will be in place for the study using a minimum of three physicians knowledgeable in the appropriate disciplines and medical specialties pertinent to the disease state being evaluated in this clinical study. This committee will be responsible for the review and adjudication to the study variables of all events identified in the CEC Charter/Manual of Operations.

The CEC will independently adjudicate to specified endpoint event definitions, event relatedness, event severity, and event outcomes.

The imaging core laboratory will be responsible for the qualitative image analysis to determine aneurysm occlusion, parent artery stenosis, and device migration. An imaging protocol will be provided to the site.

Pre-Specified Study Endpoints:

The pre-specified study endpoints and analysis listed here are the primary body of data that will be collected, analyzed, and summarized in a series of tables, lists, and graphs as part of the final report for this study. Other analysis will be conducted as part of the final report but these are the core set of analyses that will constitute the foundation of the clinical study report.

Primary endpoints:

Safety:

- Occurrence of major stroke in the territory supplied by the treated artery or neurological death post-procedure (1-year)

Effectiveness:

- Complete aneurysm occlusion (defined as Raymond-Roy grade 1) without significant parent artery stenosis ($\leq 50\%$) or retreatment of the target aneurysm post-procedure (1-year)

Secondary endpoints:

Safety:

- Occurrence of major stroke in the territory supplied by the treated artery or neurological death at 30 days post-procedure due to procedural complications
- Delayed intracerebral hemorrhage > 30 days post-procedure

Effectiveness:

- Device deployment success rate at the target site

Additional Safety Analyses:

- [REDACTED]
- [REDACTED]

- [REDACTED]
 - [REDACTED]
 - [REDACTED]

Additional Effectiveness Analyses:

- [REDACTED]
 - [REDACTED]
 - [REDACTED]
- [REDACTED]
- [REDACTED]
- [REDACTED]
- [REDACTED]
- [REDACTED]

Study Procedure:

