 - Access Site Complications
 - Procedural Systemic Complications
 - Vasospasms
- Neurological Events:
 - Focal Neurological Deficit
 - Cerebral Infraction
 - Transient Ischemic Attack (TIA)
 - Intracranial Hemorrhage (ICH)
 - Stroke
 - Death

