longer completely occluded, based on Core Lab, (i.e., residual neck or residual aneurysm is found by Core Lab) at 12 months post-procedure. This endpoint will only be defined in those subjects with both 6- and 12-month imaging adjudicated. The percentage of subjects that undergo retreatment of the target aneurysm after the initial PED treatment will also be presented. Major stroke in the territory supplied by the treated artery or neurological death at 30 days post-procedure due to procedural complications; the event and event-relatedness will be adjudicated by the CEC. The 1-year event rate will also be tabulated and reported. A binary variable, and the event will be adjudicated by the CEC.

- Intracerebral hemorrhage (ICH) > 30 days post-procedure; the event will be adjudicated by the CEC. The 1-year event rate will also be tabulated and reported. A binary variable, and the event will be adjudicated by the CEC.
- Parent artery stenosis; continuous variable from the post-procedure imaging adjudicated by Core Lab, dichotomized into >50% and ≤50% stenosis. Additionally, stenosis will be presented by quartile.
- Device migration; a categorical variable from the post-procedure imaging adjudicated by Core Lab.

The second series of **Post-Procedure** variables to be summarized will address the safety and efficacy profile over the course of the entire clinical investigation.

- The device-related neurologic adverse event rate at 1 year post-procedure will be presented with the relationship between the device and the neurologic adverse events adjudicated by the independent CEC. Disabling stroke or neurological death at 1 year (as observed)
- Ischemic and Hemorrhagic Cerebrovascular Events (as adjudicated by CEC) : includes incidence of Stroke (Major or Minor, Ipsilateral or Contralateral), Cerebral Infarction (Symptomatic or Asymptomatic), Intracranial Hemorrhage, Transient Ischemic Attack, and Target Aneurysm Rupture
- Aneurysm recurrence
- Device Related Serious Adverse Events
- Procedure related Serious Adverse Events

8. Validation Requirements

Output will be validated by level I or II validation.

Level I: The peer reviewer independently programs output and then compares the output with that generated by the original Statistical Programmer.

Level II: The peer reviewer reviews the code; where appropriate, performs manual calculations or simple programming checks to verify the output.

9. References

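### The SAP's secondary safety endpoint counts only delayed intracerebral hemorrhage, whereas the protocol specifies delayed intracranial hemorrhage, so delayed subarachnoid, subdural and epidural bleeds do not count toward it

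*SAP*

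**What the plan says.** The protocol lists the item in section 3.1 and again, in the same words, in section 9.4: "All intracranial hemorrhages and delayed intracranial hemorrhages (>30 days post-procedure". Section 21 defines the parent term: "Intra-Cranial hemorrhage is defined as hemorrhage within the fixed vault of the cranium (skull". It then has the Clinical Events Committee (CEC) sort each such event into categories. One is "Intra Cerebral Hemorrhage (further categorized as", which splits into intraparenchymal and intraventricular bleeding. The others stand beside it at the same level: "Sub Arachnoid Hemorrhage (SAH): Bleeding into the subarachnoid" space, "Subdural Hematoma (SDH): Occurs when there is tearing of the bridging vein", and epidural hematoma.

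The SAP states in section 3 that it is based on protocol revision B. In sections 5 and 7.9 it lists the secondary safety endpoint as "Delayed intracerebral hemorrhage > 30 days post-procedure". Sections 4 (objectives), 7.7 (post-procedure variables) and 7.13.3 also use the intracerebral term for the delayed event; 7.13.3 reads "Intracerebral hemorrhage (ICH) > 30 days post-procedure; the event will be adjudicated by the CEC". The SAP uses the same abbreviation differently in the section 7.9 list of CEC events of interest through 1 year: "Intracranial Hemorrhage (ICH". Its own abbreviation list in section 2 gives ICH only as the harmonisation body.

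**The concern.** The SAP's endpoint is a subset of what the protocol asks for, and the SAP neither declares nor justifies the narrowing. Section 7.12 says the planned analyses follow the clinical investigation plan, so a reader would not expect a departure here.

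The bleeds that drop out matter in this study. Protocol section 1.2.1 gives prevention of rupture, or of further hemorrhage, as the aim of treatment and names subarachnoid hemorrhage as a consequence of rupture. Protocol section 1.3 makes hemorrhagic events under dual antiplatelet therapy a study question. A delayed subarachnoid bleed from the treated aneurysm bears on the first and a delayed subdural bleed under antiplatelet therapy on the second, yet neither would be an event for the study's named delayed-bleeding endpoint. The SAP also intends to contrast the results with earlier Pipeline studies and to use them in a US indication evaluation (section 3), so a delayed-bleeding rate that is too low would carry beyond this report.

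**Working it through.** The documents give no expected rate, threshold or power for delayed hemorrhage, so there is no figure to reproduce. The check compares texts and then illustrates the size.

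**Step 1. What each definition counts after day 30**

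| Category (protocol section 21) | Protocol 3.1 / 9.4 item | SAP secondary endpoint as worded |
|---|---|---|
| Intracerebral: intraparenchymal | counted | counted |
| Intracerebral: intraventricular | counted | counted |
| Subarachnoid | counted | not counted |
| Subdural | counted | not counted |
| Epidural | counted | not counted |

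**Step 2. Is it a single slip?** No. The intracerebral term is used for the delayed event in five places (SAP sections 4, 5, 7.7, 7.9 and 7.13.3). No readable SAP text widens it.

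**Step 3. Does another planned output give the protocol's delayed rate?**

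- SAP 7.9 (CEC events of interest) and 7.13.3 (cerebrovascular events) list intracranial hemorrhage, and 7.13.3 also lists target aneurysm rupture. Neither states a split at 30 days.
- SAP 7.10 tabulates adjudicated adverse events from day 31 to study exit, but by system organ class and preferred term, without a combined intracranial row.
- GUSTO bleeding (protocol Table 6-1) puts intracerebral hemorrhage in the top grade. A subarachnoid or subdural bleed without transfusion or substantial hemodynamic compromise requiring treatment falls to Mild, whereas protocol 3.1 and 9.4 analyse Moderate and Severe.
- The primary safety endpoint requires major stroke in the treated territory or neurological death. A subarachnoid bleed that raises the NIHSS by 3 or less is a minor stroke, and subdural and epidural bleeds are not named in the stroke definition.

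**Step 4. Size, for illustration**

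Inputs: N = 200, the enrolment maximum in both documents; exact Clopper-Pearson 95% intervals, the method in SAP section 6. The event counts and subtype share are assumptions.

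- Rate = x/N, so each omitted subject changes it by 1/200 = 0.5 percentage points.
- Interval: lower limit = 0.025 quantile of Beta(x, N − x + 1); upper limit = 0.975 quantile of Beta(x + 1, N − x).
- Assume 4 subjects with a delayed intracranial bleed: 4/200 = 2.0% (0.55% to 5.04%).
- If 25% are non-intracerebral: 4 × 0.25 = 1 omitted; 3/200 = 1.5% (0.31% to 4.32%).
- If 50% are non-intracerebral: 4 × 0.50 = 2 omitted; 2/200 = 1.0% (0.12% to 3.57%).

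**The case against.** The best defence is that little is lost from safety reporting as a whole. Delayed subarachnoid, subdural and epidural bleeds would appear in the day-31-to-exit adverse event tables with subject counts, and in the intracranial hemorrhage tables through 1 year. A delayed subarachnoid hemorrhage meeting the major-stroke and territory criteria, or causing neurological death, would count in the primary safety endpoint. All of that stands and limits the point to this endpoint. It does not supply the combined delayed-intracranial rate the protocol asks for.

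Second, the protocol ranks nothing. The secondary tier is the SAP's creation, and only sections 5 and 7.9 use the label. Section 7.12 can be read as keeping the protocol's item in the plan, section 7.13.3 sits under a heading for analyses beyond the protocol, and the version history says that version 2.0 revised endpoint definitions. These readings are possible, but no visible SAP table or parameter carries the protocol's item, and nothing explains why the delayed-bleeding measure promoted to secondary is the narrower one.

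Third, the Additional Safety Analyses bullets in section 5 are redacted and the CEC charter is not available. A delayed intracranial analysis may exist there, so its absence cannot be shown. Neither source would change the wording of the named endpoint.

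Fourth, the double use of ICH suggests a terminology error, not an intended exclusion. That may well be so. A programmer would still have to follow the literal term or guess, and the same correction is needed.

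Finally, the illustrated intervals overlap heavily, and this endpoint has no threshold or decision rule; section 6 sets thresholds only for the two primary endpoints. That is correct: no formal study conclusion is shown to change.

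**Conclusion.** The concern holds for the endpoint as worded. The SAP's secondary delayed-bleeding endpoint covers two of the five bleed types that the protocol's delayed item includes, and the departure is undeclared. It can only lower the rate or leave it unchanged. The mismatch in wording is certain; its numerical effect is not, because the documents give neither a delayed-bleed rate nor a subtype split. The range of 1.0–1.5% against 2.0% rests on assuming 4 events in 200 subjects and a non-intracerebral share of 25–50%. This should be corrected because a named safety endpoint differs from its protocol in the favourable direction, although the underlying events remain visible in other tables.

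**What to change.** In SAP sections 4, 5, 7.7, 7.9 and 7.13.3, replace the delayed intracerebral term with delayed intracranial hemorrhage (more than 30 days after the procedure), as defined in protocol section 21. Report its subject-level rate with the exact 95% interval. Beneath it, show the CEC subtypes: intraparenchymal, intraventricular, subarachnoid, subdural and epidural. Keep intracerebral hemorrhage as a component row, which preserves any comparison with earlier studies that reported it. Among hemorrhage terms, use ICH only for intracranial hemorrhage, and define it so in section 2.

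The cost is SAP wording and table layout. The CEC already assigns the subtypes, so no new data or adjudication are needed. The reported rate may be slightly less favourable.

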The PUFs study was a multicenter, prospective, single-arm trial to evaluate the safety and effectiveness of the PED in complex large and giant IAs.²⁸ One hundred seven subjects with large and giant unruptured wide-necked aneurysms in the petrous to the superior hypophyseal segment of the ICA were treated with the PED. The aneurysms measured ≥ 10 mm in diameter and had either a neck ≥ 4 mm or no discernable neck. A total of 104 subjects with 106 aneurysms were included in the primary effectiveness cohort. Of the 106 aneurysms, 78 demonstrated complete occlusion without major stenosis at 180 days (73.6%; 95% posterior probability interval: 64.4%–81.0%). At one year, 86.8% (79/91) of the target aneurysms were completely occluded. This rate increased to 95.2% (59/62) complete occlusion at five years. There were no cases of aneurysm recurrence. The primary safety endpoint was the occurrence of major ipsilateral stroke or neurologic death at 180 days, which occurred in six of the 107 subjects (5.6%; 95% posterior probability interval: 2.6%–11.7%). At five year follow-up, the rate of major ipsilateral stroke or neurologic death remained 5.6%.

International Retrospective Study of the Pipeline Embolization Device (IntrePED)

The IntrePED study was a retrospective global post market study of subjects treated with the PED at 17 centers worldwide.²⁹ A total of 793 subjects with 906 aneurysms of various sizes and locations were included. The median follow-up period was 19.3 months with 89% subjects with greater than 1 year follow-up. The overall neurological morbidity rate was 7.4% (59/793) and the neurological mortality rate was 3.8% (30/793). The combined neurological morbidity and mortality rate was 8.4% (67/793). The combined neurological morbidity and mortality for treated ruptured aneurysms was higher at 18.4% (14/76). Data from the IntrePED study report the safety of the PED in the treatment of various IAs in a real-world clinical setting.

Aneurysm Study of Pipeline in an Observational Registry (ASPIRe)

ASPIRe was a prospective, multi-center, single arm, post-market registry of 191 IA patients with 207 aneurysms from 28 worldwide centers who underwent PED treatment. The 207 aneurysms in the study had a median follow-up duration of 6.6 months. The majority of aneurysms treated were saccular and overall average size of treated aneurysms was 14.5mm.

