UADE	Unanticipated Adverse Device Effect	Any serious adverse effect on health or safety or any life-threatening problem or death caused by, or associated with, a device, if that effect, problem, or death was not previously identified in nature, severity or degree of incidence in the Investigational Plan or application (including a supplementary plan or application), or any other unanticipated serious problem associated with a device that relates to the rights, safety, or welfare of subjects.
ULN	Upper Limit of Normal	Upper limit within a particular range.
USADE	Unanticipated Serious Adverse Device Effect	Serious adverse device effect which by its nature, incidence, severity or outcome has not been identified in the current version of the risk analysis report.

3. Introduction

This document provides a detailed description of the statistical methods and procedures to be implemented during the analysis of the SHIELD study. The methods and procedures described in this document are intended to support the generation of a Clinical Study Report (CSR) for Clinical Protocol NV-PED-10, including detailed descriptions of the populations, methodologies, post-text tables, analysis summary tables, patient data listings, and descriptive graphics. The information collected during this clinical investigation will be used to assess specific parameters and contrast these results with other Pipeline studies where the Pipeline device did not have the Shield Technology™. Likewise, the information analyzed herein will help us to assess safety and efficacy of the device for, but not limited to, a US indication evaluation.

This study is a multi-country, prospective, single-arm, multi-center clinical investigation evaluating outcomes in subjects with intracranial aneurysms who are treated with the Pipeline™ Flex Embolization Device with Shield Technology™. Within this current study, the safety and effectiveness of the Pipeline™ Flex Embolization Device with Shield Technology™ device in subjects undergoing treatment for intracranial aneurysms will be analyzed.

Subjects will be considered enrolled in the study once the patient has signed and dated the Informed Consent or DRF and the Pipeline™ Flex Embolization Device with Shield Technology™ is advanced into the micro catheter inside the patient.

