The patient will be tested at the discretion of the site per standard of care procedures for antiplatelet response and the appropriate dose of antiplatelet agents will be given after the Pipeline™ device with Shield Technology™ placement procedure. Medications could be continued as medically indicated.

Estimated Duration of Patient Participation

Up to 200 subjects will be enrolled over a period of approximately 24 months. The study is intended to have 200 subjects undergo attempted deployment of the Pipeline™ device with Shield Technology™. Each study patient will be followed for 1 year after the primary study procedure. Study participation includes consent, initial screening and baseline, treatment using the Pipeline™ device with Shield Technology™, discharge exam and follow-up visits at approximately 30, 90, 180 days, and 1 year. The total study duration is expected to be approximately 3 years.

Schedule of Assessments

	Baseline	Procedure	Discharge	1 Month	3 Months	6 Months	1 Year	Unscheduled
Schedule		Day 0		±14 days	±30 days	±6 weeks	±8 weeks	
Eligibility	X							
Demographics	X							
Aneurysm Symptoms	X	O	O	O	O	O	O	OR
Medical History		X						
Study Procedure		X						
Procedure Imaging		XR						
Ancillary Devices		X						
Study Device		XR						
Discharge			X					
Follow Up				X	X	X	X	XR
Follow-Up Imaging				OR	OR	OR	OR	OR
NIHSS	O	X		O	O	O	O	OR
mRS	O	X		O	O	O	O	OR
Exit			X					

Retreatment Study Procedure				OR	OR	OR	OR	OR
Labs	OR	OR	O	O	O	O	O	OR
Device Specific Event		OR	OR	OR	OR	OR	OR	OR
Adverse Event Assessment		OR	OR	OR	OR	OR	OR	OR

Key: Required=X Optional=O Repeatable=R

ANALYSIS POPULATIONS

The following populations will be considered for the analysis of data for this study:

Intent to Treat (ITT)

The Intention to Treat (ITT) population includes all consented subjects in whom deployment of the Pipeline™ device with Shield Technology™ was attempted.

Full Analysis Set (FAS)

The Full Analysis Set (FAS) population is a subset of the ITT population including only those subjects in whom the Pipeline™ device with Shield Technology™ was implanted.

Internal Carotid Artery (ICA) Population

The Intra-Cranial Artery Population (ICA) is a subset of the ITT population including only those subjects in whom the Pipeline™ device with Shield Technology™ was implanted in the ICA (segments C2-C7).

Non-ICA Population

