The non-ICA is a subset of the ITT population including only those subjects in whom the Pipeline™ device with Shield Technology™ was implanted in the arterial vessels other than those specified in the ICA population.

6. Determination of Sample Size

No formal estimates were prepared for examining the individual variables. However, the incidence of certain events will be examined relative to the thresholds used in research treating a similar population. Device outcomes variables recorded on a dichotomous scale will be summarized using a 2-sided 95% Clopper-Pearson exact binomial confidence interval. The upper and lower bounds of the confidence interval will be examined relative to results in the peer-reviewed literature and studies using the

Pipeline device without the Shield Technology™. Specifically, the incidence at 1 year post-procedure of a major stroke in the territory supplied by the treated artery or neurological death will be examined relative to an a priori threshold of 15%. The incidence at 1 year post-procedure of aneurysm occlusion without significant parent artery stenosis will be examined relative to an a priori threshold of 50%.

7. Statistical Methods

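### The SAP's only stated way to contrast SHIELD with earlier uncoated Pipeline studies uses an interval that carries SHIELD's sampling error alone, so it is too narrow for a between-study contrast

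*SAP*

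**What the plan says.** The SAP introduction (section 3) states the aim to "contrast these results with other Pipeline studies where the Pipeline device did not have the Shield Technology™". SAP section 6 then gives the method. "Device outcomes variables recorded on a dichotomous scale will be summarized using a 2-sided 95% Clopper-Pearson exact binomial confidence interval". The section goes on to say how that interval is to be used: "The upper and lower bounds of the confidence interval will be examined relative to results in the peer-reviewed literature and studies using the" uncoated device.

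The same paragraph goes on to two fixed benchmarks for the primary endpoints at 1 year. For safety, major stroke in the treated territory or "neurological death will be examined relative to an a priori threshold of 15" per cent. For effectiveness, occlusion "without significant parent artery stenosis will be examined relative to an a priori threshold of 50" per cent.

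The readable text has no interval for a difference, no pooling of the earlier results and no allowance for their sampling error. SAP sections 7.7 and 7.9 add only one-sample limits and proportions. Some of the additional analyses are blacked out and cannot be judged. Protocol section 9.2 proposes no formal success criteria, and SAP section 7.13.1 says that there is no formal testing strategy.

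**The concern.** A one-sample interval suits a comparison with a fixed constant. Earlier Pipeline results are estimates, several of them from about 100 patients or aneurysms. Protocol section 1.2.3 prints the PUFs safety rate as 6/107 with an interval of 2.6% to 11.7%. It also reports that "78 demonstrated complete occlusion without major stenosis at 180 days" out of 106 aneurysms, with an interval of 64.4% to 81.0%. Setting SHIELD's limits beside 5.6% or 73.6% drops that uncertainty.

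At stake is what is said about Shield against no Shield. SAP section 3 foresees regulatory submissions and manuscripts. A sentence there saying that SHIELD's interval lies below the PUFs rate would look like evidence of a difference when the data of the two studies together might not support one.

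**Working it through.** **Inputs.** SHIELD n = 200, from SAP section 5: "The study is intended to have 200 subjects undergo attempted deployment of the Pipeline™ device with Shield Technology™". This is a maximum. The comparators are assumed to be those in Protocol section 1.2.3, because the SAP names none. The common true rate p is assumed equal to each study's observed rate.

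**1. Reproduce the printed intervals.** The equal-tailed 95% limits of Beta(x+1, n−x+1) give 2.6% to 11.7% for 6/107 and 64.4% to 81.0% for 78/106. Both match the protocol.

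**2. How much too narrow.** With a comparator of size m and equal rates:

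SE(difference) / SE(SHIELD alone) = sqrt[p(1−p)/200 + p(1−p)/m] / sqrt[p(1−p)/200] = sqrt(1 + 200/m).

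For m = 107 this is sqrt(2.869) = 1.69. In points, for PUFs safety, the normal-approximation 95% half-width goes from 3.2 for SHIELD alone to 5.4 for the difference.

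**3. Chance of exclusion when the true rates are equal.** Sum Bin(x; 200, p) × Bin(y; m, p) over all pairs (x, y) for which y/m falls outside the Clopper-Pearson interval for x/200. The last column repeats this, counting instead the pairs for which the Newcombe 95% interval for the difference excludes zero.

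| Comparator result | Count | sqrt(1+200/m) | One-sample interval excludes earlier rate | Newcombe interval excludes zero |
|---|---|---|---|---|
| PUFs, major ipsilateral stroke or neurological death | 6/107 | 1.69 | 22.3% | 4.5% |
| PUFs, occlusion without major stenosis, 180 days | 78/106 | 1.70 | 23.4% | 5.1% |
| PUFs, complete occlusion, 1 year | 79/91 | 1.79 | 25.5% | 4.8% |
| ASPIRe, neurological morbidity and mortality | 13/191 | 1.43 | 14.9% | 4.5% |
| ASPIRe, complete occlusion, last visit | 77/103 | 1.72 | 23.9% | 5.0% |
| IntrePED, neurological morbidity and mortality | 67/793 | 1.12 | 6.2% | 4.8% |

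Normal check: 2 × [1 − Φ(1.96/1.69)] = 24.7% for PUFs safety. The exact figure is lower because Clopper-Pearson is conservative: against a truly fixed rate, the same interval misses only 2.9% to 4.5% of the time in these settings. A smaller SHIELD sample changes little: 21.1% for PUFs safety at n = 180, and 22.1% for PUFs 1-year occlusion at n = 160.

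**4. Example on the closest endpoint.** Suppose SHIELD has 4/200 = 2.0%. Clopper-Pearson gives 0.5% to 5.0%, wholly below PUFs' 5.6%. The Wilson limits are 0.78% to 5.03% for SHIELD and 2.60% to 11.70% for PUFs. Newcombe for the difference of −3.61 points:

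- lower = −3.61 − sqrt[(2.00−0.78)² + (11.70−5.61)²] = −9.8
- upper = −3.61 + sqrt[(5.03−2.00)² + (5.61−2.60)²] = +0.7

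The interval for the difference includes zero. Four is the largest SHIELD count that lies wholly below 5.6%, so this is a boundary case. In the other direction, 19/200 (5.8% to 14.4%) lies wholly above 5.6%, yet the difference is +3.9 points (−3.0 to +9.6).

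**5. The fixed thresholds.** The interval clears 15% with at most 19/200 events (one-sided error 1.5%) and clears 50% with at least 115/200 successes (2.0%). It is the right tool there.

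**The case against.** The best defence is that SAP section 6 only says the bounds will be examined relative to earlier results. It gives no inclusion or exclusion test and no rule for calling Shield better or worse, and both documents describe the study as descriptive. This stands. The percentages in the table are error rates of a reading that a user may adopt, not of a rule in the plan. It does not remove the point, because a descriptive contrast still needs an interval for the contrast, and none is offered.

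A reader might infer three stronger things that the documents do not support:

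- **That the 15% and 50% thresholds are mishandled, or offered as proof of similarity to uncoated Pipeline.** They are fixed numbers for which a one-sample interval is correct, and the SAP makes no similarity claim from them.
- **That a US indication rests on this contrast.** SAP section 3 mentions the US indication in a separate sentence about safety and efficacy generally.
- **That a two-sample interval can be applied to every count printed in the protocol.** Most do not match SHIELD's endpoints. PUFs 78/106 is at 180 days, PUFs 79/91 is occlusion alone, ASPIRe 77/103 is at last visit, and the ASPIRe and IntrePED safety figures are neurological morbidity and mortality. The mismatch can outweigh sampling error. A SHIELD result of 160/200 (73.8% to 85.3%) differs from the PUFs 180-day result by +6.4 points (−3.2 to +16.8) and from the PUFs 1-year result by −6.8 points (−15.0 to +3.0).

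It is also fair to say that against IntrePED the problem is slight.

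**Conclusion.** The point holds as a should-fix. For a contrast that the SAP itself announces, the only stated uncertainty is SHIELD's own, understated by a factor of 1.12 (IntrePED) to 1.79 (PUFs, 1 year). If exclusion is read as a difference, chance alone produces one in about 22% to 25% of cases against PUFs, 15% to 24% against ASPIRe and 6% against IntrePED, rather than in at most 5%.

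This rests on comparators that the SAP does not name, SHIELD at its maximum of 200, and equal true rates at the earlier observed values. SHIELD's own rates, their intervals and the threshold readings are unaffected, which is why it is not a must-fix.

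**What to change.** In SAP section 6:

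- Keep the one-sample Clopper-Pearson interval for SHIELD's own rates and for the 15% and 50% thresholds.
- Name the comparator studies. Where endpoint and time point reasonably match, report the SHIELD-minus-comparator difference with a two-sample 95% interval (Newcombe or Miettinen-Nurminen), labelled unadjusted and descriptive. Among the counts in the protocol, PUFs 6/107 is the closest match. It is a 180-day result, and the protocol says that the rate was still 5.6% at five years.
- Where nothing matches, show the earlier result with its own interval and state the mismatch.
- Draw no statement that Shield is better or worse from the one-sample interval alone.

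The cost is a few sentences and a few lines of code, with no new data. For safety, the observed-data tabulation already planned in SAP section 7.4 supplies a SHIELD count. The price is wider intervals and weaker comparative statements. The two-sample interval does not correct for differences in case mix.
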